8.3.1.1.2. Definition of Serious Adverse Event

A SAE is defined as any untoward medical occurrence that at any dose:

- Results in death,
- Is life-threatening; this means that the subject was at risk of death at the time of the event; it does not mean that the event hypothetically might have caused death if it were more severe,
- Requires in-patient hospitalization or prolongation in existing hospitalization,
- Results in persistent or significant disability/incapacity or substantial disruption of the ability to conduct normal life functions,
- Is a congenital anomaly/birth defect, or
- Is another important medical event (see below).

Important medical events that do not result in death, are not life-threatening or do not require hospitalization may be considered SAEs when, based on appropriate medical judgment, they may jeopardize the subject and may require medical or surgical intervention to prevent one of the outcomes listed above. Examples of such medical events include allergic bronchospasm requiring intensive treatment in an emergency room or in a physician's office, blood dyscrasias or seizures

that do not result in in-patient hospitalization, and the development of drug dependency or drug abuse.

A distinction should be drawn between serious and severe AEs. Severity is a measure of intensity whereas seriousness is defined by the criteria above. For example, a mild degree of gastrointestinal bleeding requiring an overnight hospitalization for monitoring purposes would be considered a SAE but is not necessarily severe. Similarly, an AE that is severe in intensity is not necessarily a SAE. For example, alopecia may be assessed as severe in intensity but would not be considered a SAE.

Medical and scientific judgment should be exercised in deciding if an AE is serious and if expedited reporting is appropriate.

8.3.1.2. Recording of Adverse Events

Adverse events should be collected and recorded for each subject from the date the ICF is signed until the end of their participation in the study, i.e. the subject has discontinued or completed the study.

Adverse events may be volunteered spontaneously by the subject, or discovered by the study staff during physical examinations or by asking an open, non-leading question such as 'How have you been feeling since you were last asked?' All AEs and any required remedial action will be recorded. The nature of AE, date (and time, if known) of AE onset, date (and time, if known) of AE outcome to date, severity and action taken of the AE will be documented together with the Investigator's assessment of the seriousness of the AE and causal relationship to study drug and/or study procedure.

All AEs should be recorded individually in the subject's own words (verbatim) unless, in the opinion of the Investigator, the AEs constitute components of a recognized condition, disease or syndrome. In the latter case, the condition, disease or syndrome should be named rather than each individual symptom. The AEs will subsequently be coded using the Medical Dictionary for Regulatory Activities (MedDRA).

8.3.1.3. Assessment of Adverse Events

Each AE will be assessed by the Investigator about the categories discussed in the following sections.

8.3.1.3.1. Intensity

The Investigator will assess all AEs for severity in accordance with the following standard ratings.

- Mild: Ordinarily transient symptoms, does not influence performance of subject's daily activities. Treatment is not ordinarily indicated.
- Moderate: Marked symptoms, sufficient to make the subject uncomfortable. Moderate
 influence on performance of subject's daily activities. Treatment may be necessary.
- Severe: Symptoms cause considerable discomfort. Substantial influence on subject's daily activities. May be unable to continue in the study and treatment may be necessary.

When changes in the intensity of an AE occur more frequently than once a day, the maximum intensity for the event should be noted for that day. Any change in severity of signs and symptoms over a number of days will be captured by recording a new AE, with the amended severity grade, and the date (and time, if known) of the change.

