During the study lorazepam may be administered for anxiety/agitation or to aid sleep; from other medications to manage insomnia, known as z-drugs, zolpidem is preferred and allowed. Lorazepam and zolpidem are not to be used in close temporal proximity (administration within 4h of each other). In addition, benzatropine/biperiden may be administered for treatment of extrapyramidal side effects and propranolol may be administered for treatment of akathisia. Lorazepam, zolpidem, benzatropine/biperiden and propranolol are allowed according to the instructions outlined in Table 5 below. Within the daily and weekly limits shown in Table 5, lorazepam, zolpidem, benzatropine/biperiden, and propranolol are permitted upon the Investigator or designee decision and are allowed on a PRN (as needed) basis.

If the patient's condition will require administration of higher dose of lorazepam, zolpidem, benzatropine/biperiden, or propranolol (exceeding the limits given in Table 5), it must be recorded as Serious Adverse Event (SAE).

The adverse event (AE) associated with the need for lorazepam, zolpidem, benzatropine/biperiden, or propranolol should be recorded on the AE eCRF. The amount and timing of each lorazepam, zolpidem, benzatropine/biperiden, or propranolol administration should be recorded for each patient in the eCRF.

Table 5 Restrictions on the Use of Lorazepam, Zolpidem, Benzatropine/Biperiden, and Propranolol during the Study

Medication	Study Period	Dosage Allowed	Timing Restrictions
Lorazepam	Screening Period and Treatment Period to Day 28, inclusive	Maximum of 6 mg/day AND	Not within 8 hours prior to PANSS, CGI-S, CGI-I or C-SSRS, BACS Not within 4 h of zolpidem administration
		Maximum 6 times/week (at least 1 day break between weeks)	
	Follow up period – Since Day 29 and onwards	According to SmPC	
Zolpidem	Screening Period and Treatment Period to Day 28, inclusive	Maximum of 10 mg/day	Not within 8 hours prior to PANSS, CGI-S, CGI-I or C-SSRS, BACS Not within 4 h of lorazepam administration
		Maximum 4 times/week	
	Follow up period – Since Day 29 and onwards	According to SmPC	
Benzatropine	Screening Period to Day 28, inclusive	Maximum of 4 mg/day	Not within 8 hours of BACS, ESRS
Biperiden		According to SmPC	
Propranolol	Screening Period to Day 28, inclusive	Maximum of 40 mg/day	

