10.11. Safety Analyses

10.11.1. Adverse Events

All AEs will be listed. The number and percent of subjects experiencing an event will be tabulated for each SOC and preferred term. The AEs will also be tabulated according to intensity and causality. An overview table presenting the incidence of AE will be presented. All tables will be prepared separately by number of patients and number of events.

Serious AEs will be listed separately.

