4.8.1. Adverse event analysis

Any undesirable signs, symptoms or medical conditions occurring or worsening of pre-existing conditions between signing informed consent and the first administration of the study medication are considered as pre-treatment AEs. Undesirable signs, symptoms or medical conditions or worsening of pre-existing conditions occurring after the first administration of study medication are considered as treatment emergent adverse events (TEAEs).

A TEAE will be analyzed as related to study medication (i.e. as adverse drug reaction, ADR) if the relationship to study treatment was documented as 'unlikely', 'possible', 'probable', or 'definite' or if the relationship to study treatment is missing.

An overview table presenting the incidence of the following AE categories will be presented. Percentage of patients in each category will be compared between treatments as a difference in proportions between treatments including a 95% CI based on the Agresti – Caffo method (2000):

- All AEs
- Pre-treatment AEs
- Serious AEs (SAEs) (including pre-treatment SAEs)
- Treatment emergent AEs (TEAEs)
- Treatment emergent SAEs (TESAEs)
- Severe TEAEs
- Related TEAEs
- Related severe TEAEs
- TEAEs leading to reduction of dose
- TEAEs leading to interruption of dose
- TEAEs leading to permanent discontinuation (i.e. withdrawal) of study medication
- Related TEAEs leading to permanent discontinuation of study medication
- AEs leading to death (i.e. outcome of AE is fatal)
- TEAEs leading to death
- Related TEAEs leading to death

All treatment emergent AEs (TEAEs) and all serious TEAEs will be tabulated by MedDRA SOC and PT presenting the number and percentage of patients reporting the AE and the number of AEs reported. Additional tables will distinguish the events by whether the AE was related to study medication and by maximum severity.

All AEs documented in the eCRF will be listed by patient. Data listings will include patient ID, treatment group, verbatim term, preferred term, system organ class, start and stop date and relative day of the AE, severity, medications (yes/no), seriousness, action taken with study medication, relationship to study medication, and outcome will be provided. TEAEs will be flagged as such. In addition, separate listings for all SAE's, deaths and AEs leading to discontinuation (action taken with study treatment = drug withdrawn, or AE is reason for early termination) will be presented.

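### Severity changes open new AE records, and the SAP has no rule to link them: episodes are counted more than once, and a washout AE that only improves can become a TEAE

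*Protocol*

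**What the plan says.** **Recording.** Protocol 8.3.1.3.1 states: "Any change in severity of signs and symptoms over a number of days will be captured by recording a new AE", and the new record comes "with the amended severity grade, and the date (and time, if known) of the change". Neither phrase is limited to worsening. The one exception concerns fluctuation within a day, which is reduced to a single daily grade: "When changes in the intensity of an AE occur more frequently than once a day, the maximum intensity for the event should be noted".

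**Collection window.** Protocol 8.3.1.2 states: "Adverse events should be collected and recorded for each subject from the date the ICF is signed". Protocol 8.3.1.1.1 confirms that untoward events in treatment-free periods, screening included, are AEs. The washout in Protocol 4.1 lasts up to 7 days and falls inside this window.

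**Classification.** The TEAE definition in SAP 4.8.1 has two limbs. The first covers undesirable signs, symptoms or conditions that occur after first dose. The second reads: "worsening of pre-existing conditions occurring after the first administration of study medication are considered as treatment emergent adverse events (TEAEs").

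**Counting.** The SAP 4.8.1 tables by system organ class and preferred term are described as "presenting the number and percentage of patients reporting the AE and the number of AEs reported". Protocol 10.11.1 adds: "All tables will be prepared separately by number of patients and number of events". The SAP overview table compares the percentage of patients in each AE category between treatments, with 95% Agresti-Caffo intervals. The categories include TEAEs and related TEAEs.

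**Timing.** Protocol 10.15 and SAP 3.6 lock and unblind the data up to Day 28 for efficacy. The safety analysis follows later, after the follow-up visits and the full lock.

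**The concern.** The recording rule and the counting rule were written separately and do not fit together. The Protocol uses a new AE record to track the course of an existing event. The SAP treats a record as an event. Two errors can follow.

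1. **Multiple counting.** One episode that moves between grades over several days contributes as many events as it has grades in sequence.
2. **Misclassification.** An AE that began in washout and eases after Day 1 gains a record with an on-treatment date. That record fits the first limb of the TEAE definition even though nothing emerged or worsened on treatment.

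The first error affects event counts only. The second also affects patient counts, and so reaches the percentages that the SAP compares with confidence intervals. It can reach the related categories too, because SAP 4.8.1 treats a relationship that is unlikely or missing as related.

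If the gap is noticed only when the safety tables are built, treatment codes will already be open, and the linking rule would be chosen with that knowledge.

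**Working it through.** The plan gives no figure on this point, so there is nothing to reproduce. The check follows the rules through example episodes and then illustrates the effect on patient incidence.

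**Step 1: events per episode.** *As written* means one record per multi-day grade, and each record dated on or after Day 1 is a TEAE. *Linked* means one event per episode, counted as a TEAE only if the highest grade after first dose exceeds the highest grade before it. The episodes are invented for illustration.

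| Episode (grade and day of change) | Records | TEAEs as written | TEAEs linked |
|---|---|---|---|
| Moderate Day -3, mild Day 4, resolved Day 9 | 2 | 1 | 0 |
| Severe Day -3, moderate Day 3, mild Day 6, resolved Day 9 | 3 | 2 | 0 |
| Moderate Day -3, mild Day 3, moderate Day 10, mild Day 14, resolved Day 20 | 4 | 3 | 0 |
| Mild Day -3, moderate Day 4, mild Day 8, resolved Day 12 | 3 | 2 | 1 |
| Mild Day 2, moderate Day 4, mild Day 6, resolved Day 9 | 3 | 3 | 1 |

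In the last two rows the patient counts once either way, and only the number of events is wrong. In the first three rows the patient is counted as having a TEAE when no grade on treatment exceeded the pre-dose grade.

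**Step 2: patient incidence.** Let p be the true proportion of patients with a TEAE. Let w be the proportion, among patients without a true TEAE, whose screening or washout AE improves through a lower grade after first dose. Then:

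recorded incidence = p + (1 - p)w, so the excess is (1 - p)w.

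Neither p nor w is in the documents. I assume p from 40% to 60% and w from 5% to 20%.

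- Smallest excess: (1 - 0.60) x 0.05 = 0.02, or 2 percentage points.
- Largest excess: (1 - 0.40) x 0.20 = 0.12, or 12 percentage points.
- Middle case: 0.50 + 0.50 x 0.10 = 0.55. With 55 patients per arm that is 27.5 rising to about 30.3 patients.

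This applies to any arm with those values of p and w. It says nothing about a difference between arms.

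**Step 3: does another rule already prevent this?**

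- The maximum-severity tables in SAP 4.8.1 select a grade for display. They do not merge records, change TEAE status or correct the number of AEs.
- The blind data review in SAP 3.3 and 4.2 is assigned protocol deviations and allocation to analysis populations. Linking AE records is not among its stated tasks.
- SAP 4.1.5 imputes partial or missing AE start dates. It does not deal with successive records of one episode.

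**The case against.** The strongest reply is that the SAP's second limb speaks of worsening, so its authors did not mean improvement to count, and a sensible programmer would not flag an eased washout AE. That is probably the intention. But an eased AE arrives in the data as a separate record with an on-treatment date, the first limb covers it, and no rule removes it. The second limb also names no reference grade. In the third episode above, the return from mild to moderate is a worsening against the latest grade but not against the washout grade.

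Other objections limit the scope, and they stand:

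- Protocol 8.3.1.1.1 sends illnesses present before study entry to medical history unless they worsen in the Treatment Period. Protocol 8.3.1.2 records a recognised syndrome rather than each symptom. Much agitation or insomnia already present at entry therefore has no AE record to split. The problem is confined to AEs that arise after consent, and washout may be shortened or omitted for unmedicated patients.
- Splitting an episode that starts on treatment does not alter the patient percentages the SAP compares. Event counts are descriptive.
- AE listings show dates, severity and the TEAE flag, so split records can be recognised. The eCRF may also link them; the documents do not say.

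A reader might infer that each dose of rescue medication generates an AE. Protocol 5.4.3 does not say so. It asks for "The adverse event (AE) associated with the need for lorazepam" and the other listed drugs to be recorded, and logs the amount and timing of each administration separately. One AE can cover many doses.

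A reader might also infer that an effective dose is charged with spurious TEAEs because its patients improve more. The between-arm excess would be carry-over x (down-grade rate on active - rate on placebo). With 20-50% carry-over and rates of 60% and 40%, it is 4 to 10 points. With equal rates it is 0, and with the rates reversed it is -4 to -10. The documents support none of these values. The direction is open too: full resolution opens no new record, while partial or fluctuating response opens several.

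**Conclusion.** The point holds as a counting and classification error built into the rules as written. A mild, moderate, mild episode on treatment counts as three events instead of one. A washout AE that never exceeds its pre-dose grade gives one to three TEAEs in the examples, where none emerged. These results need only a literal reading of both documents.

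Event counts are inflated in all arms, and patient-level TEAE and related-TEAE percentages can be. The 2 to 12 point range is an illustration under assumed p and w, not an estimate for this trial. No bias against active treatment is shown. The matter is worth settling because it enters a comparison reported with confidence intervals, the correction is cheap, and the planned order of analyses unblinds before safety is analysed.

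**What to change.** Add to SAP 4.8.1, before the unblinding at the Day 28 lock:

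1. Contiguous records of the same episode are linked, through an eCRF link where one exists, or otherwise by the same preferred term with contiguous dates, decided under blind.
2. Each linked episode is counted once, at its maximum severity, in all tables of events and patients.
3. An episode with onset before first dose is treatment-emergent only if its severity after first dose exceeds its worst pre-dose grade.
4. All severity-change records stay in the listings.

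Protocol recording need not change and no data are lost. The cost is one derivation step plus some manual linking under blind if the eCRF has no link field. One consequence should be accepted openly: an episode that had eased before first dose and returns only to its earlier worst grade will not count as a TEAE and will be visible only in the listings.

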8.3.1.3.2. Causality

The Investigator will assess the causality/relationship between the study drug and the AE. One of the categories described in Table 7 should be selected based on medical judgment, considering the definitions below and all contributing factors.

Table 7 Assessment of Relationship of Adverse Events to Investigational Product

Related	A clinical event, including laboratory test abnormality, occurs in a plausible time relationship to treatment administration, and which concurrent disease or other drugs or chemicals cannot explain. The response to withdrawal of the treatment (dechallenge*) should be clinically plausible. The event must be definitive pharmacologically or phenomenologically, using a satisfactory rechallenge† procedure if necessary.	
Probably related	A clinical event, including laboratory test abnormality, with a reasonable time sequence to administration of the treatment, unlikely to be attributed to concurrent disease or other drugs or chemicals, and which follows a clinically reasonable response on withdrawal (dechallenge). Rechallenge information is not required to fulfil this definition.	
Possibly related	A clinical event, including laboratory test abnormality, with a reasonable time sequence to administration of the treatment, but which could also be explained by concurrent disease or other drugs or chemicals. Information on treatment withdrawal may be lacking or unclear.	
Unlikely to be related	A clinical event, including laboratory test abnormality, with a temporal relationship to treatment administration which makes a causal relationship improbable, and in which other drugs, chemicals or underlying disease provide plausible explanations.	
Unrelated	A clinical event, including laboratory test abnormality, with little or no temporal relationship with treatment administration. May have negative dechallenge and rechallenge information. Typically explained by extraneous factors (e.g., concomitant disease, environmental factors or other drugs or chemicals).	

^{*}Dechallenge is when a drug suspected of causing an AE is discontinued. If the symptoms of the AE disappear partially or completely, within a reasonable time from drug discontinuation, this is termed a positive dechallenge. If the symptoms continue despite withdrawal of the drug, this is termed a negative dechallenge. Note that there are

[figure not shown]
exceptions when an AE does not disappear upon discontinuation of the drug, yet drug-relatedness clearly exists (for example, as in bone marrow suppression, fixed drug eruptions, or tardive dyskinesia).

†Rechallenge is when a drug suspected of causing an AE in a specific subject in the past is readministered to that subject. If the AE recurs upon exposure, this is termed a positive rechallenge. If the AE does not recur, this is termed a negative rechallenge.

8.3.1.4. Reporting of Serious Adverse Events

The Investigator will review each SAE and evaluate the intensity and the causal relationship of the event to study drug. All SAEs will be recorded from signing of the ICF until the final Follow-up Visit. Serious AEs occurring after the final Follow-up Visit and coming to the attention of the Investigator must be reported only if there is (in the opinion of the Investigator) reasonable causal relationship with the study drug.

The Investigator is responsible for providing notification to the Sponsor of any SAE, whether deemed IMP-related or not, that a subject experiences during their participation in study within 24 hours of becoming aware of the event.

As a minimum requirement, the initial notification should provide the following information:

- Study number,
- Patient number,
- Sex,
- Date of birth,
- Name of Investigator and full clinical site address,
- Details of SAE,
- Criterion for classification as 'serious',
- Study drug name, or code if unblinded, and treatment start date,
- Date of SAE onset,
- Causality assessment (if sufficient information is available to make this classification).

The Sponsor will request clarification of omitted or discrepant information from the initial notification. The Investigator or an authorized delegate is responsible for sending via email the requested information to the Sponsor within 24 hours of the Sponsor's request.

Initial reports of SAEs must be followed later with detailed descriptions, including clear photocopies of other documents as necessary (e.g. hospital reports, consultant reports, autopsy reports), with the subject's personal identifiers removed. All relevant information obtained by the Investigator through review of these documents will be recorded and emailed to the Sponsor within 24 hours of receipt of the information. If a new SAE report form is emailed, then the Investigator must sign and date the form. The Sponsor may also request additional information on the SAE, which the Investigator or an authorized delegate must send via email to the Sponsor within 24 hours of the request.

8.3.1.5. Reporting of Suspected Unexpected Serious Adverse Reaction

Information on SUSARs will be collected and reported to the regulatory authority and the IEC in accordance with European Commission Guidance 2011/C 172/01 or as per national regulatory requirements in the participating country. Details of reporting on country level will be described in the Safety Management Plan.

